**OBJECTIVES:**

**Purpose**

The primary purpose of the study is to determine the effect of sleep deprivation on neural responses to food odors in the early olfactory and reward-related brain regions, and how these effects are related to appetite-regulating hormones. We will further examine how altered neural responses to food translate to enhanced appetite and food intake, and which brain processes support resilience to sleep-dependent increases in food intake. We will use appetitive food odors in combination with functional magnetic resonance imaging (fMRI) and pattern-based data analysis to test the effects of sleep deprivation on neural responses to food. We will also examine effects of sleep deprivation on appetite levels, odor pleasantness, and *ad-libitum* calorie intake.

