**2) Aim 2: Determine the link between sleep-dependent olfactory processing and calorie intake.**

Sleep-restriction has been shown to enhance craving and consumption of high-calorie snacks. Here we aim to determine the relationship between altered hormone levels, neural processing of food odors, and enhanced calorie intake. *We hypothesize that fMRI responses in early olfactory and reward-related brain regions will mediate enhanced food craving and calorie intake. Moreover, we predict that brain processes related to resilience will be represented in the dorsolateral prefrontal cortex, and that these processes are characterized by enhanced connectivity with reward-related brain regions.* After the fMRI scanning session, satiated subjects will be given the opportunity to consume high-calorie snacks *ad libitum* in a controlled environment. In addition, subjects' food intake will be recorded for 24 after the scanning session using dietary diaries. We will compute the total calorie intake and compare it between

sleep-deprived and non-deprived states. Critically, we will use neural mediation analyses to determine how the relationship between sleep-dependent changes in hormone levels and enhanced calorie intake is mediated by neural responses to food odors. This will reveal brain regions in which neural processing of food mediates increased food intake, and thereby identify potential therapeutic targets. We also propose to compare subjects that manage to abstain from excess calorie intake in a sleep-deprived state to those that do not. This will identify brain processes that support resilience to enhanced calorie intake. We predict that such processes will be represented in the dorsolateral prefrontal cortex and will be characterized by enhanced inhibitory connectivity with reward-related regions. Identification of these protective mechanisms may inform future clinical studies in obesity, and may help to establish novel treatment and prevention strategies for weight-gain and obesity, specifically in high-risk populations with disrupted sleep-schedules.

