### **BACKGROUND:**

About one-third of adults in the US get insufficient sleep ( $\leq 6$  h per night; 7 h recommended) (1). Habitual sleep deprivation has been associated with adiposity and obesity in both clinical and epidemiological studies (2, 3). A primary reason for weight gain with inadequate sleep is excessive consumption of calories beyond the homeostatic energy requirement (4). Specifically, experimentally induced sleep deprivation increases the desire for foods high in sugar and fat content (5-7), and is related to excessive consumption of calories, especially from energy dense snacks (8, 9). A decline in sleep, paralleled by a steep rise in obesity rates has made it critical to understand the mechanistic link between chronic sleep deprivation and weight gain.

[figure not shown]
Sleep-deprivation has been shown to alter appetite-regulating hormones in humans (10, 11). In particular, sleep deprivation is associated with an increased availability of orexigenic hormones, such as ghrelin (10) and the *endocannabinoids* (2-arachidonoylglycerol (2-AG) and 2-oleoylglycerol (2-OG)) (11). However, how these hormonal alterations affect central processing of food stimuli, and how they result in enhanced food intake with sleep debt is not well understood in humans. Interestingly, studies suggest that orexigenic hormones may regulate appetite and food intake by altering olfactory sensitivity (12-14), hence leading to increased perception and intake of food (15). This would suggest that early olfactory cortices are among the first stages in the neural processing hierarchy at which sleep deprivation alters processing of food-related stimuli.

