## PROCEDURES INVOLVED:

We propose to implement a randomized within-subject, crossover partial sleep-deprivation protocol to examine the effects of sleep deprivation (SD) on neural processing of food odors in early sensory and reward-related brain regions. In brief, after a one-week sleep stabilization period, subjects will spend a night either sleep deprived (SD, 4 h of sleep) or with normal sleep (non-SD, NDS, 8 h of sleep) at home. On the next day, fMRI scanning will be conducted at 7 pm after dinner, when sleep-deprivation induced changes in hormonal levels are most prominent (11). Hormone levels will be monitored using serial blood sampling in response to a meal (dinner).

**Sleep-deprivation protocol.** Subjects (N=40) will be randomly assigned to either participate in the SD or the NSD condition first (**Fig. 2A**). Subjects will then undergo a sleep stabilization phase to stabilize circadian rhythms. During this week, subjects will be instructed to keep a regular sleep schedule of 7-9 hours in bed between 10:30 pm and 7:30 am. Participants will abstain from alcohol, caffeine, and drugs in this phase. After the sleep stabilization week, the night before the fMRI session, subjects will either sleep normally (NSD, 8 h of sleep between 11 pm and 7 am), or sleep only for 4 h between 1 am and 5 am (SD) at home. We opted for a partial sleep-deprivation protocol because this situation (late bedtime and early wakeup) is ecologically valid as it reflects the most realistic form of sleep-deprivation in

everyday life. All subjects will participate in both sleep conditions (SD and NSD) in randomized order, separated by a 2.5-week washout period.

*Sleep-monitoring.* To ensure that subjects follow the sleep schedule during the sleep stabilization phase and sleep manipulation days, we will record sleep duration, as well as sleep and wake-up time using a daily sleep diary and wrist actigraphy (ActiGraph, LLC, Pensacola, Florida (45)). Additionally, subjects will rate their subjective sleep quality, alertness, and restfulness every morning using an online questionnaire. Subjects will also rate their subjective sleepiness using the Stanford Sleepiness Scale (46) before the fMRI scan during both the SD and NSD phase. Participants will spend the night of sleep manipulation (both SD and NSD) at home and food will be provided for these days.

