*fMRI scanning protocol.* On the first day of the study, before being assigned to the SD or NSD phase, subjects will rate the pleasantness of six food odors, including three high caloric sweet (caramel, yellow cake, ginger bread) and three high caloric savory odors (potato chips, pot roast, garlic butter). Based on each participant's ratings, we will select two sweet and two savory odors matched in rated pleasantness. We will also include two control non-food odors (fir and celery seed). On the day of fMRI scanning, subjects will arrive at the imaging center at 6 pm and will consume a dinner before entering the scanner. This pre-feeding will satisfy metabolic hunger (i.e., energy requirements), and thus render the fMRI measures more sensitive to sleep-dependent changes in hedonic hunger, i.e., food intake exceeding energy requirements (47). During fMRI data acquisition, odors will be delivered directly to the subject's nose via a MR-compatible olfactometer. Neuroimaging will be performed at the Northwestern University Center for Translational Imaging (CTI) on a state-of-the-art Siemens PRISMA system with a 64 channel head coil, using imaging sequences optimized for signal recovery in olfactory and orbitofrontal cortices (48). Specifically, subjects will perform 4 runs of an odor detection task inside the MRI scanner while blood oxygen-level dependent (BOLD) responses will be acquired with high spatial (2 mm isotropic) and temporal resolution (2000 ms). On each trial, subjects will be cued to sniff, and an odor corresponding to one of the three experimental groups (sweet, savory, non-food) or clean air will be delivered pseudo-randomly. Subsequently, subjects will rate the pleasantness or the intensity (pseudo-randomized) of the delivered odor. Sniffing behavior will be monitored using an MR-compatible breathing belt and a spirometer. A high-resolution anatomical image will be acquired for the purpose of spatial normalization and anatomical localization of the fMRI responses.

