*Hormone levels.* As soon as subjects arrive at the imaging center, an intravenous sterile heparin-lock catheter will be inserted in a forearm vein and blood sampling will be initiated by the CRU mobile nurse. We will draw blood every 30 min after arrival, resulting in 5 samples, including a fasted baseline (6 pm), after dinner (6:30 pm), before (7 pm), during (7:30 pm, after the second scanning run), and after the scanning session (8 pm) for leptin and ghrelin analysis. An additional sample will be collected at 7:30 pm time point for 2-AG and 2-OG analysis. Plasma and serum samples will be frozen at  $-80^{\circ}\text{C}$  until assay for ghrelin, leptin, insulin using commercially available ELISA kits, and 2-AG and 2-OG using published procedures (49, 50). Phase of menstrual cycle in women has an impact on these hormonal levels. The 2.5-week washout period will ensure that the blood samples are collected in the same phase of the menstrual cycle

*Ad-libitum food intake.* At the completion of the fMRI scan, participants will be provided with snacks in a

buffet-style setting where they will have *ad libitum* access to food items corresponding to the odors used during fMRI scanning (sweet and savory high-calorie snacks). They will be instructed to consume as much food as they like. To measure food intake, food will be weighed pre- and post- consumption, and calories consumed will be calculated. Because subjects have been provided with dinner before the scanning session, food intake at the buffet will mainly reflect hedonic, rather than metabolic eating (47). *Appetite and hunger ratings.* Subjective food craving, ratings of hunger, fullness, prospective food consumption, and satiety will be measured using a visual analogue scale. These ratings will be acquired on the fMRI scanning day upon arrival, at all blood collection time points, and after the *ad libitum* meal. Subjects will also complete the food craving questionnaire on the day of fMRI scan.

*24 h post-fMRI food intake diary.* Subjects will be instructed to carefully record the food items, quantity consumed, place of consumption, and the food brands, for 24 h following the fMRI scan. We will calculate the total energy, fat and carbohydrate consumption for SD and NSD states.

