#### **DATA AND SPECIMEN MANAGEMENT:**

Sample size is based upon the requirements for group analysis, particularly when random-effects analyses are performed. Random-effects analyses require a minimum of 14 -18 subjects in each group in order to obtain statistically meaningful fMRI effects. Our target subject number also accounts for attrition in the subject pool due to unanticipated claustrophobia, technical/mechanical issues, or other problems during the fMRI session.

For the statistical analyses, comparisons of subjective appetite ratings and calorie intake between the SD and NSD state will be carried out using paired t-tests. Spearman's correlation analysis will be used to test the relation between appetite ratings, neural responses to food odors, and the total calories consumed. Moreover, we will use whole-brain mediation analysis (51) to identify the brain regions in which neural responses to food odors mediate the link between sleep-dependent changes in hormone levels and enhanced calorie intake. To identify brain mechanisms related to resilience, we will compare fMRI responses to food odors between subjects that manage to abstain from excess calorie intake in a sleep-deprived state to those that do not. We will use fMRI connectivity analyses (psychophysiological interaction, PPI (52)) to test the hypothesis that resilience to enhanced food intake in a SD state is associated with enhanced functional connectivity between the dorsolateral prefrontal cortex and reward-related brain regions (53). We will monitor sniffing using a breathing belt and spirometer, and model trial-by-trial sniff parameters will be included as covariates in all fMRI analyses following established procedures to control for respiration-induced effects.

To preserve subject privacy and confidentiality, all research materials (questionnaires, behavioral testing results, and magnetic resonance imaging data) will be coded by a different study code number unique for each subject, in order to keep the identity and personal information of each subject as confidential as possible. This number will be recorded on all testing sheets instead of the subject's

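### Resilience is tested by comparing two groups whose cut-off and intake measure are not given, although each completer has a continuous intake change that would serve better if the relation is graded.

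*Protocol*

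**What the plan says.** Aim 2 of the Protocol states: "We also propose to compare subjects that manage to abstain from excess calorie intake in a sleep-deprived state to those that do not". The statistical paragraph under Data and Specimen Management repeats the contrast: "we will compare fMRI responses to food odors between subjects that manage to abstain from excess calorie intake in a sleep-deprived state to those" who do not. Neither place says how much eating is excess, against what level, or on which measure.

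Two intake measures are available under Procedures Involved. For the buffet after the scan, "To measure food intake, food will be weighed pre- and post- consumption, and calories consumed will be calculated". For the 24 h diary, "We will calculate the total energy, fat and carbohydrate consumption for SD and NSD states". Both are listed as secondary endpoints. Both can be compared within a subject, because "All subjects will participate in both sleep conditions (SD and NSD) in randomized order".

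On the reference level, the Purpose section asks "which brain processes support resilience to sleep-dependent increases in food intake", Aim 2 compares intake between the two sleep states, and the SAP (Analysis of food intake) expresses change as a percentage of the NSD session. The SAP uses that change only for a one-sample test against zero.

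The same Protocol paragraph also plans Spearman correlations of neural responses with calories consumed, and a whole-brain mediation analysis with intake as the outcome. Neither is named as the resilience analysis. The connectivity (PPI) hypothesis says that resilience is associated with stronger prefrontal-reward coupling, without saying whether resilience enters as a group or as a score.

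**The concern.** There are two linked problems.

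- **Who is in each group.** Without a cut-off and a named intake measure, different analysts could form different groups from the same data.
- **Whether groups are the right tool.** Every completer has a graded SD-NSD change in intake. Reducing it to two categories treats a subject just above the cut like one far above it. If the neural response varies steadily with the change, the contrast is less likely to detect the relation than a regression on the score.

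The hypothesis matters to the sponsor: Aim 2 presents protective mechanisms as a possible guide to prevention and treatment. It is also a between-subject question, so it gains nothing from the within-subject pairing that helps the SD-NSD comparisons.

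**Working it through.** The documents give no alpha, effect size, cut-off or group size for this contrast, so there is no planned figure to reproduce. The check compares analyses under stated assumptions.

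**Inputs from the documents**
- Enrolment of 40 and expected drop-out of 15-25% (Protocol, Number of Local Participants). Completers: 40 × 0.75 = 30 to 40 × 0.85 = 34.

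**Assumptions**
- The SD-NSD intake change is normal, and its relation to the neural measure is linear with correlation r.
- There is one uncorrected two-sided test at 5%.

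**Step 1: information kept by a split.** If a share f of subjects falls below the cut, a two-group comparison keeps a fraction equal to the squared correlation between score and label. This is below 1 for any cut, because a two-valued label cannot reproduce a continuous score. For a normal score the fraction is φ(z_f)² / [f(1 − f)].

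- Median split, f = 0.5: 0.3989² / 0.25 = 0.637. The 30 / 34 completers then count as about 30 × 0.637 = 19 and 34 × 0.637 = 22.
- Cut at zero change, with an assumed mean increase of 0.5 SD: f = Φ(−0.5) = 0.309, so 0.3521² / (0.309 × 0.691) = 0.58. The 30 / 34 completers count as about 17 and 20. Abstainers number about 30 × 0.309 = 9 or 34 × 0.309 = 10 to 11, fewer than the 14 to 18 per group that the Protocol itself gives as a minimum for random-effects analyses.

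These fractions depend on the shape of the score and are not bounds. A median split keeps 75% of the information for a uniform score and 48% for an exponential one.

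**Step 2: simulated power.** Methods: t test of the correlation, t test of the rank correlation, and two-sample t test on each split.

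| Analysis | r = 0.5, N = 30 | r = 0.5, N = 34 |
|---|---|---|
| Continuous change | 0.83 | 0.87 |
| Rank-based | 0.77 | 0.82-0.83 |
| Median split | 0.61 | 0.67 |
| Cut at zero change (mean increase 0.5 SD) | 0.57 | 0.63 |

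With weaker relations the order of continuous score and median split is the same. At r = 0.4 power is 0.61 / 0.67 continuous against 0.41 / 0.46 split. At r = 0.3 it is 0.37 / 0.42 against 0.25 / 0.27.

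**Step 3: the case that favors groups.** Suppose that the response depends only on which side of a population cut the subject lies, with half on each side and a label-response correlation of 0.5.
- Split at the true cut: 0.85 / 0.89. Continuous score: 0.63 / 0.69.
- Split at the sample median instead of the true cut: 0.70 / 0.77.
- Step at the 30% point but split at the median: 0.45 / 0.50, against 0.57 / 0.63 for the continuous score.

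Grouping therefore wins when there is a step and the cut falls on or near it. The Protocol gives no cut.

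**The case against.** The strongest reply is that the plan can be read sensibly as it stands, and that graded analyses of intake are already in it.

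- **The reference level is reasonably clear.** This largely stands. A reader might infer a contradiction, because the Background speaks of "excessive consumption of calories beyond the homeostatic energy requirement" and the pre-feeding rationale of "sleep-dependent changes in hedonic hunger, i.e., food intake exceeding energy requirements". Neither passage defines the resilience groups. The passages that do concern resilience, and the SAP's change score, point to own NSD intake. What remains is that the groups are not explicitly tied to it.
- **No median split is proposed.** This is correct. A reader might take the median-split loss as the cost of the plan, but the documents do not say that the sample will be halved. Eating no more than in the NSD state is the more natural rule. It does not rescue the contrast: the zero-change cut does slightly worse in the illustration.
- **Graded analyses exist.** They do, so the graded information is not lost to the study. However, the Spearman analysis is described on calories consumed rather than on the SD-NSD change, and neither it nor the mediation analysis is assigned to resilience.
- **The supplied SAP may be incomplete.** Its pre-processing section points forward to connectivity and univariate analyses that the supplied text does not show. The point therefore rests on the contrast that the Protocol describes, not on the SAP's silence.
- **Post hoc choice of the cut.** A reader might infer that the cut will be picked after looking at the results. Nothing in the documents says so.
- **Absolute power.** The only imaging threshold shown is family-wise corrected, so these powers do not carry over to the imaging tests. They serve to compare the analyses.

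**Conclusion.** The concern holds in a limited form. The Protocol frames resilience as a two-group contrast without a cut-off or a named intake measure, and leaves the reference level implicit. A continuous change is available for every completer.

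Under a linear relation, grouping loses power at any cut. In the illustration at r = 0.5 the loss is 0.83 − 0.61 = 0.22 at N = 30 and 0.87 − 0.67 = 0.20 at N = 34 for a median split. It is 0.83 − 0.57 = 0.26 and 0.87 − 0.63 = 0.24 for a cut at zero change. These sizes rest on an assumed r, a normal score, an assumed mean increase for the zero cut, and one uncorrected test; the documents supply none of these. If resilience is a true step at a known cut, the direction reverses.

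Resilience is an Aim 2 hypothesis and not a listed endpoint, so the primary results are untouched. The change is worth making because it replaces a weaker method at almost no cost; it does more than fill in a missing definition.

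**What to change.** Make the main resilience analysis a second-level regression over all completers. The outcomes are (a) the SD-minus-NSD food-odor response and (b) the PPI connectivity between dorsolateral prefrontal cortex and reward regions. The regressor is the continuous SD-NSD change in intake.

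- Name one intake measure, buffet or diary, for the main analysis. Either can be defended.
- State the scale of the change. If the SAP's percentage change is used, say how zero NSD intake is handled, since the percentage is then undefined.
- Add a rank-based sensitivity analysis, because intake change may be skewed.
- Keep the two-group contrast as secondary, with cut-off, reference level and measure fixed before the resilience data are examined. The SAP is written in the past tense; if those data have already been seen, label the analysis exploratory.

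The cost is one regressor and a few sentences, with no new data. The regression assumes a graded relation and ranks those who eat less when sleep-deprived as the most resilient, which may not be what the investigators mean. It also loses power if resilience is a step at a known cut (0.63 against 0.85 at N = 30). The rank analysis and the pre-defined secondary contrast limit this only in part.

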**PROVISIONS TO MONITOR THE DATA TO ENSURE THE SAFETY OF PARTICIPANTS:**

This study does not involve more than minimal risk to the participants and therefore this section is not applicable.

**WITHDRAWAL OF PARTICIPANTS:**

Subjects will be informed at the onset of the study that they are free to terminate the study for any reason whatsoever. They will be assured that such a decision will not influence their treatment or relationships with health care providers at the Northwestern Medical Faculty Foundation or Northwestern Memorial Hospital. If the subject is a student or employee of Northwestern University, they will be informed that participation will not adversely affect their class ranking or employment status.

Any participant that experience adverse event during the study, which makes it no longer safe to for the individuals to participate problems, will be withdrawn from the study without their consent. Any unanticipated problems will be reported to the IRB in accordance with posted guidance. In addition, if a participant fails to follow the procedure he/she will be excluded from the study.

